### Title of Trial:

A Phase 3, Randomized, Double-Blind, Placebo Controlled, Multi-Center Trial to Evaluate the Efficacy and Safety of DaxibotulinumtoxinA for Injection to Treat Moderate to Severe Glabellar Lines (SAKURA-2)

Trial Center(s):	Up to 15 centers in the United States (US) and Canada
Number of Subjects Planned:	Approximately 300 subjects will be enrolled
Trial Period:	Up to 38 weeks, including 2 weeks for screening
Phase of Development:	3

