### **Design and Methodology:**

This is a Phase 3, randomized, double-blind, placebo-controlled, multi-center trial. Approximately 300 adult subjects with moderate to severe glabellar lines will be enrolled. Subjects will be randomly assigned in a 2:1 ratio to DaxibotulinumtoxinA for Injection 40 U or placebo.

All subjects will be followed for at least 24 weeks post-treatment for efficacy and safety assessments. If both Patient Frown Wrinkle Severity (PFWS) and Investigator Global Assessment Frown Wrinkle Severity (IGA-FWS) scores at maximum frown, return to baseline by the Week 24 visit or at a visit between Weeks 24 and 36, the visit at which that score is recorded will be the Final Evaluation Visit for the subject.

After the Final Evaluation Visit, all qualified subjects will have the option to enroll into an open-label, trial to evaluate the long-term safety of repeat use of DaxibotulinumtoxinA for Injection for the treatment of moderate to severe glabellar lines.

The Investigator, trial center staff, subjects, and Sponsor will remain blinded to study treatment throughout the trial. Only the statistician responsible for the randomization codes will be unblinded to the treatment assignments.

Treatment Group	Test Article and Dose	No. of Subjects	
Treatment 1	DaxibotulinumtoxinA for Injection 40 U	200	
Treatment 2	Placebo	100	

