#### 7.5.1 PRIMARY EFFICACY ENDPOINT

Primary clinical efficacy will be assessed by the blinded evaluator who will grade the severity of the subject's glabellar lines at maximum frown using the IGA-FWS and the subject who will grade the severity of their glabellar lines at maximum frown using the PFWS. A response is defined as achieving a score of 0 or 1 (none or mild) and an improvement of at least two points from the baseline, on both the IGA-FWS and PFWS scales concurrently at the time point of evaluation. With both IGA-FWS and PFWS using a 4-point scale and the target population having a score of 2 or 3 (moderate or severe) at baseline, achieving an improvement of at least two points is inclusive in the status of achieving a score of 0 or 1 (none or mild). Henceforth, the response defined here will be abbreviated as "2-point composite response."

The proportion of subjects who have a 2-point composite response at Week 4 will be compared between daxibotulinumtoxinA and placebo using the Cochran–Mantel–Haenszel (CMH) test stratified by trial center using a two-sided test with a Type I error rate of 0.05.

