## 7.5.5 HANDLING MISSING DATA AND OTHER CONSIDERATIONS

Missing Data
For endpoints that are a composite and/or derived from study assessments, imputation of missing data will be performed on the original assessments first.
No imputations will be utilized for the PP analyses.
As needed, a model-based multiple imputation approach may be explored to assess the impact of different imputation methods on the trial outcomes.
Pooling Data
Most of the efficacy endpoints are analyzed with trial center as a stratification factor. The trial is intended to be conducted in a manner such that a minimum of 5 ITT subjects in each treatment group will be enrolled at each trial center/site. In the event that there are too few subjects in a treatment arm at a single site, this site will be combined with another to achieve the desired minimum sample size per arm.

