7.5.6 SENSITIVITY AND SUBGROUP ANALYSES
The robustness of main analysis results for the primary and secondary endpoints will be evaluated via sensitivity analyses on the per-protocol population and on data with missing values imputed using different approaches, such as no imputation (observed data only) or when necessary, multiple imputation.
Statistical tests will be conducted to identify if there are extreme trial centers that could affect the interpretation of common statistical and clinical conclusions. A CMH test of the primary efficacy endpoint will be conducted with factors of treatment group stratified by trial center.

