## 7.7 SAMPLE SIZE AND POWER CONSIDERATIONS

Estimates of treatment efficacy taken from trial RT002-CL002 show that a sample size of
200 and 100 for DaxibotulinumtoxinA 40 U for injection and placebo, respectively,

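### The only visible test named for finding extreme trial centers repeats the primary CMH test, which does not test whether centers differ

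*Protocol*

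**What the plan says.** Protocol 7.5.6 (Sensitivity and Subgroup Analyses) gives the aim: "Statistical tests will be conducted to identify if there are extreme trial centers that could affect the interpretation of common statistical and clinical conclusions". The sentence that follows is the only one in the visible section to name a test for that aim: "A CMH test of the primary efficacy endpoint will be conducted with factors of treatment group stratified by trial center".

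Protocol 7.5.1 sets the primary analysis of the 2-point composite response at Week 4 as a CMH "test stratified by trial center using a two-sided test with a Type I error rate of 0.05".

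On layout, the synopsis allows "Up to 15 centers in the United States (US) and Canada", and allocation is 2:1. Protocol 7.7 gives "200 and 100 for DaxibotulinumtoxinA 40 U for injection and placebo, respectively". Protocol 7.5.5 intends that "a minimum of 5 ITT subjects in each treatment group will be enrolled at each trial center/site" and pools sites that fall short.

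The visible SAP adds no center comparison. Section 4.6.1 says the primary analysis is repeated as a sensitivity analysis, but how is not visible. Section 4.9.1 plans no covariate adjustment.

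**The concern.** The aim and the method do not match. Endpoint, treatment factor, strata and test in 7.5.6 are those of 7.5.1, and no different population or imputation is named for this check. Read literally, it returns the primary p-value a second time. That p-value would be tiny in a successful trial however much the centers disagreed, and it could be reported as evidence that no center was extreme.

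The protocol has reason to look. Response depends on subjective ratings by the investigator and the subject at each site, and product is prepared and injected at each site. A rating or preparation problem confined to one center is the kind of thing the first sentence of the check is meant to find.

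**Working it through.** **1. What there is to reproduce.** The response rates and power behind the sample size are not visible, so the plan offers no figure to reproduce. Every response rate below is an assumption.

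**2. Layout.** 300 subjects / 15 centers = 20 per center. At 2:1 that is about 13 active and 7 placebo.

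**3. What the CMH statistic measures.** In a center with n1 active and n0 placebo subjects, N = n1 + n0, *a* active responders and *m* responders in all:
- expected active responders: e = n1·m/N
- variance: v = n1·n0·m·(N − m) / (N²(N − 1))
- statistic: (Σ(a − e))² / Σv, on 1 df.

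Deviations are summed over centers before squaring. Disagreement between centers is averaged away, and no center is identified.

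**4. Fixed example (15 centers of 13:7).** Every center has 9/13 active responders. Placebo is 1/7 in five centers and 0/7 in ten.
- Placebo 1/7: m = 10, e = 6.5, a − e = 2.5, v = 91·10·10/7600 = 1.197.
- Placebo 0/7: m = 9, e = 5.85, a − e = 3.15, v = 91·9·11/7600 = 1.185.
- Sums: 5(2.5) + 10(3.15) = 44.0; Σv = 17.841. CMH = 44.0²/17.841 = **108.5**.

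*One center fails completely.* Change one of the ten to 0/13 and 0/7. Then m = 0, so that center contributes nothing to either sum: (44.0 − 3.15)²/(17.841 − 1.185) = 40.85²/16.655 = **100.2**.

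*One center is reversed.* Change one of the five to 0/13 active and 5/7 placebo. Then m = 5, e = 3.25, a − e = −3.25, v = 91·5·15/7600 = 0.898. CMH = (44.0 − 2.5 − 3.25)²/(17.841 − 1.197 + 0.898) = 38.25²/17.541 = **83.4** (p about 7e-20).

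With the reversed center, a Breslow-Day test (Tarone correction) moves from 8.6 to 82.3 on 14 df, p about 1e-11. The CMH p-value gives no warning.

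**5. CMH in simulation.** Layouts were 15 centers of 13:7 and 10 of 20:10, with drug 50 or 70%, placebo 2 to 10%, two-sided 0.05 and 1,500 runs per scenario. CMH rejected in 100% of runs when all centers agreed, when one had no effect and when one was reversed. With three reversed centers it still rejected in 83 to 100%.

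The statistic can even rise while a center fails. At placebo 2%, the median was 124 with all centers at 70% on drug. It was 133 with one center at 0% and fourteen at 75%, which is the same average (14 × 75%/15 = 70%).

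**6. A homogeneity test instead.** If placebo response is near zero, center odds ratios often do not exist. The chance of no placebo responder among 7 is 0.98⁷ = 0.87, 0.95⁷ = 0.70 or 0.90⁷ = 0.48 at placebo rates of 2, 5 and 10%. In the step 5 runs Breslow-Day/Tarone found a single no-effect center in only 15 to 40%. A permutation test of center risk differences (15 centers of 13:7, placebo 2 to 10%) gave:

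| Situation | CMH rejects | Homogeneity test rejects |
|---|---|---|
| All centers agree | 100% | 4–5% |
| One center 0% on drug | 100% | 83–100% |
| Seven centers 90%, eight 50% | 100% | 86–97% |
| One center 35% on drug | 100% | 18–24% |
| One center 100% on drug | 100% | 15–26% |

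**7. How far the 83–100% depends on the drug rate.** I repeated the one-center-at-0% case using the sum of squared deviations of the 15 center differences, with responses reshuffled between centers within arm (499 reshuffles, 1,000 trials per scenario). Over placebo 2 to 10% it rejected in 86–100% with the other centers at 75%, 73–98% at 70%, and 29–49% at 50%. If the failing center's drug response equals the placebo rate rather than zero, the figure with the others at 75% is 63–100%. CMH rejected in every scenario.

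**The case against.** The strongest objection is redaction. Section 7.5.6 speaks of tests in the plural and its title covers subgroups, yet one center test and no subgroup text survive. SAP 4.9 runs from 4.9.1 straight to 4.9.5, and the method in SAP 4.6.1 is blank. A reader might infer that the plan has no analysis of center differences anywhere. The documents do not support that, because a suitable test could sit in removed text. What stands is narrower: the sentence that names the CMH test is complete and visible, and the test does not serve the aim stated just before it.

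A second objection is that the alternative is no sure detector. A reader might infer that a homogeneity test would catch any odd center, since it can reject in nearly all runs for gross departures. Steps 6 and 7 do not support that: power is low for one moderately deviating center and depends on the drug response elsewhere. Nor would comparing drug-arm response across centers be enough. It ignores placebo and reacts to case mix: with a common odds ratio and placebo at 1% in eight centers and 5% in seven, it rejected in 92% of runs.

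Third, this is a supporting analysis, and center data can be examined afterwards from what is collected. That is true and limits the severity. A check specified before unblinding still carries more weight than one chosen later.

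**Conclusion.** Wrong as written, within a limited scope. The only visible named test for extreme centers duplicates the primary analysis and does not test whether centers differ. The identity of the two tests follows from the text and rests on no assumption. The simulation figures rest on assumed response rates, equal center sizes and up to 15 centers. The CMH result held over the whole range tried, whereas the power of the replacement varies widely within it.

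The primary test, its alpha and the sample size are unaffected. A reader might take the point as casting doubt on the primary comparison; nothing in the documents supports that.

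**What to change.** Replace the CMH sentence in Protocol 7.5.6, and carry the change into the SAP before unblinding, with:

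1. A homogeneity test of the center-specific Week 4 risk differences, with centers pooled as in 7.5.5, in a permutation or exact version.
2. A leave-one-center-out re-estimate of the primary risk difference with its confidence interval. This shows which center matters and by how much. A plot of center differences is optional.
3. A statement that, at about 20 subjects per center, the test has low power for a single moderately low or implausibly good center, so a non-significant result is not evidence that centers agree.

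If redacted text already specifies a suitable test, it is enough to name it in 7.5.6 in place of the CMH. The cost is a few sentences and a short program, with no new data and no change to the primary analysis.

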#### 7.6 SAFETY ANALYSES

#### 7.6.1 ADVERSE EVENTS

Safety summaries and analyses will be performed on the safety population. Descriptive statistics will be presented to summarize the safety data.

All AEs will be recorded and classified on the basis of MedDRA terminology. Treatment-emergent AEs are those AEs with an onset on or after the date and time of study treatment. All treatment-emergent AEs will be summarized by treatment group, system organ class, preferred term, severity, relationship, and seriousness.

Comparisons between treatment groups will be made by tabulating the frequency of subjects with one or more treatment-emergent AEs (classified into MedDRA terms) from baseline (post-treatment) to Week 4 as well as from baseline (post-treatment) through the duration of the trial.

Serious adverse events (SAEs) will be listed by subject. SAEs will be summarized by treatment group, severity, and relationship to study treatment. Each subject will be counted only once within a system organ class or a preferred term using the event with the greatest relationship and greatest severity.

All information pertaining to AEs noted during the trial will be listed by subject, detailing the verbatim description given by the Investigator, preferred term, system organ class, start date, stop date, severity, action taken regarding study drug, corrective treatment, outcome, and drug relatedness. The event onset will also be shown relative (in number of days) to the date of first study treatment administration. In addition, a list of subjects who prematurely discontinue from the trial due to adverse events will also be provided.

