### 3.1.1 DURATION OF TRIAL

The duration is up to 38 weeks on trial, including a screening period of up to two weeks followed by a single treatment and a follow-up period of up to 36 weeks post-treatment. All subjects will be followed for at least 24 weeks post-treatment.

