# 4.2.5 FINAL EVALUATION VISIT OR EARLY DISCONTINUATION

The following procedures must be performed and recorded at the Final Evaluation Visit for each subject. Following treatment, subjects will be followed for safety until at least Week 24 and up to Week 36 with monthly visits until both IGA-FWS and PFWS scores have returned to baseline. The subject will then have a Final Evaluation Visit.

- 1. Conduct patient education: Discuss the potential effect of DaxibotulinumtoxinA for Injection treatment, explain the PFWS measurement and the categories of the severity assessment scales, and instruct the subjects to consider depth of lines for severity of their glabellar lines. Use the provided Patient Education Brochure
- 2. Measure and record vital signs (body temperature, respiratory rate, sitting radial pulse, and sitting systolic and diastolic blood pressure)

If there are no safety concerns, the subject's participation in the trial is complete at this visit.

After the Final Evaluation Visit, all qualified subjects will have the option to enroll into an open-label, trial to evaluate the long-term safety of repeat use of DaxibotulinumtoxinA for Injection for the treatment of moderate to severe glabellar lines.

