3.3. Safety Assessments

3.3.1. Adverse Events

All adverse events (AEs) will be recorded and classified on the basis of MedDRA terminology. AE severity will be graded as mild, moderate, or severe as defined in Section 6.1.2 of the protocol. AEs with an onset on or after the date and time of study treatment will be Treatment-emergent.

The safety endpoints derived from the AEs are:

- Frequency, severity and relationship to study drug of treatment-emergent adverse events during the first four weeks post treatment and the overall study duration
- Frequency, severity and relationship to study drug of treatment-emergent serious adverse events during the first four weeks post treatment and the overall study duration

	İ			

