4.8.3. Adverse Events

All treatment-emergent AEs (TEAEs) will be listed and summarized by treatment group, system organ class, preferred term, severity, relationship, and seriousness. Serious adverse events (SAEs) will be summarized by treatment group, severity, and relationship to study treatment and will be listed by patient separately.

Each patient will be counted only once within a system organ class or a preferred term using the event with the greatest relationship and greatest severity.

Specific AF will be summarized by treatment group, system organ class, and preferred term. Adverse events included will be those listed in the query from Section 3.3.2.

All information pertaining to AEs noted during the trial will be listed by patient, detailing the verbatim description given by the Investigator, preferred term, system organ class, start date, stop date, severity, action taken regarding study drug, corrective treatment, outcome, and drug

relatedness. The event onset will also be shown relative (in number of days) to the date of first study treatment administration. In addition, a list of patients who prematurely discontinue from the trial due to adverse events will also be provided.

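### Whole-trial adverse event percentages are compared between arms although follow-up after Week 24 depends on the efficacy outcome, so the drug arm's figure is likely to be inflated

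*Protocol*

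**What the plan says.** **Follow-up.** The protocol synopsis (Design and Methodology) sets a minimum: "All subjects will be followed for at least 24 weeks post-treatment for efficacy and safety assessments". Protocol 3.1.1 sets the maximum: "a follow-up period of up to 36 weeks post-treatment". Between the two, Protocol 4.2.5 keeps subjects in follow-up "until both IGA-FWS and PFWS scores have returned to baseline", and under the synopsis "the visit at which that score is recorded will be the Final Evaluation Visit for the subject". SAP 2.1 repeats the rule. Protocol 6.1 collects adverse events until the subject's own participation ends, and Protocol 6.2 asks about them at every visit.

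**Analysis.** Protocol 7.6.1 makes the between-arm comparison by tabulating subjects with one or more treatment-emergent events over two windows: "from baseline (post-treatment) to Week 4 as well as from baseline (post-treatment) through the duration of the trial". Protocol 7.3 and SAP 3.3.1 name the corresponding safety endpoints, for all events and for serious events, "during the first four weeks post treatment and the overall study duration". SAP 4.8.3 states "All treatment-emergent AEs (TEAEs) will be listed and summarized by treatment group" and counts each patient once per term; the readable text of that section sets no time window. SAP 4.8.1 describes exposure by injected volume only. The readable text contains no Week 24 cut-off, no rate per unit of follow-up time, no time-to-event method for adverse events and no summary of follow-up length by arm.

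**The concern.** After Week 24, how long a subject is observed depends on whether the treatment effect has worn off, and so on the arm. A placebo subject who never improved meets the exit condition at Week 24. A drug subject with remaining effect does not, and gains up to 12 more weeks at risk and up to three more adverse event queries (Weeks 28, 32 and 36).

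A crude percentage of subjects with at least one event rises with observation time. Two arms with the same risk per week would then show different whole-trial percentages, and a reader could take the difference for late toxicity. The endpoint affected is one the plan names, and the planned exposure summary would not reveal the imbalance.

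**Working it through.** The documents give no figure to reproduce: they state no adverse event risk and no share of subjects staying past Week 24.

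**Inputs from the documents.** Minimum follow-up is 24 weeks and maximum 36, a gap of at most 36 − 24 = 12 weeks and a ratio of at most 36/24 = 1.5. Planned arm sizes are 200 and 100.

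**Assumptions (not in the documents).** The hazard of a first event is the same in both arms. p is the risk of at least one event by Week 24. A share f of the drug arm stays to Week 36 and the rest leave at Week 24. All placebo subjects leave at Week 24 unless stated. Nobody drops out before Week 24.

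**Constant hazard.** Risk by Week 36 = 1 − (1 − p)^(36/24). Crude drug percentage = (1 − f)·p + f·[1 − (1 − p)^1.5].

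With p = 30%: 1 − 0.70^1.5 = 41.4%. At f = 30%, 0.7 × 30.0 + 0.3 × 41.4 = 33.4%.

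| Share of drug arm staying to Week 36 | Mean drug follow-up (weeks) | Placebo | Drug | Spurious excess (points) |
|---|---|---|---|---|
| 10% | 25.2 | 30.0% | 31.1% | 1.1 |
| 30% | 27.6 | 30.0% | 33.4% | 3.4 |
| 50% | 30.0 | 30.0% | 35.7% | 5.7 |
| 100% (bound) | 36.0 | 30.0% | 41.4% | 11.4 |

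For p from 5% to 50%, the excess is 0.7 to 4.4 points at f = 30% and 1.2 to 7.3 points at f = 50%.

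**Some placebo subjects stay.** If 10% of placebo also stay to Week 36, placebo shows 31.1%. The excess at p = 30% falls from 5.7 to 4.6 points (f = 50%) and from 3.4 to 2.3 points (f = 30%).

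**Events cluster early.** Suppose 20% are affected by Week 4 and 30% by Week 24. The later hazard is −ln(0.70/0.80)/20 = 0.00668 per week. Risk by Week 36 is 1 − 0.70·exp(−12 × 0.00668) = 35.4%. The excess is 1.6 points at f = 30% and 2.7 at f = 50%, with a bound of 5.4.

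**Rare events.** With an assumed 1% serious event risk by Week 24, 1 − 0.99^1.5 = 1.50%. The bound is 0.5 points. At f = 30% the excess is 0.15 points, about 0.3 of 200 subjects.

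**Check of the remedies under equal hazards.** Counting onset through Week 24 gives 30.0% in both arms in every case above. A rate per person-time (to first event) gives −ln(0.70)/24 = 1.486 per 100 person-weeks in both arms if the hazard is constant. It does not if events cluster early. In that example the hazard to Week 4 is −ln(0.80)/4 = 0.0558, and mean time at risk through Week 24 is 0.20/0.0558 + 0.10/0.00668 = 18.6 weeks. Placebo therefore has 0.30/18.6 = 1.62 per 100 person-weeks. With f = 50%, the drug arm adds 0.5 × 0.0539 = 0.027 events and 0.027/0.00668 = 4.0 weeks, giving 0.327/22.6 = 1.45. The bias has changed sign.

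**The case against.** The strongest reply is that little depends on this table. Safety is summarised descriptively, and the readable text attaches no test or decision rule to adverse events. The Week 4 comparison already uses an equal window and covers the period right after a single injection. Events are also tabulated by severity and relationship, and onset day is listed for every event, so a late excess could be traced. The bias makes the drug look worse, so the crude table cannot hide harm. All of this stands and limits the severity. It does not make the whole-trial percentages comparable, and a by-subject listing is not a between-arm comparison.

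A reader might go further than the documents allow in four ways:

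- **Placebo follow-up is 24 weeks.** This is an inference. A placebo subject scoring below baseline on either scale stays longer.
- **An excess of about 11 points is to be expected.** That figure needs every drug subject to stay to Week 36 and no placebo subject to stay. It is a bound, and the floor is near 0.
- **Serious events are materially distorted.** At low risks the absolute effect is a fraction of a point.
- **The plan certainly makes no allowance.** Parts of the SAP's safety and analytical-issues text are not readable, and its table shells are not available here. A windowed table or a follow-up summary could be in them. Protocol 7.6.1, which sets out the comparison, is readable and has neither.

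**Conclusion.** The concern holds as a point that should be fixed, judged on the readable text. The exit rule and the whole-trial comparison together give an observation window that is likely to be longer on drug, with no visible correction, and so a drug percentage biased upward under equal risks.

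A plausible size is a few points: 3.4 to 5.7 with 30% to 50% of the drug arm staying, under a constant hazard and a 30% risk by Week 24, or 1.6 to 2.7 if events cluster early. The direction is firm whenever more drug than placebo subjects stay past Week 24. The size is not, because p, f, the hazard shape and the placebo share staying are all assumed. The primary efficacy analysis and the Week 4 safety tables are untouched.

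**What to change.** In SAP 4.8.3, and in Protocol 7.6.1 if the protocol is amended for other reasons:

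1. Add a between-arm table of treatment-emergent events with onset from treatment through Week 24, and make it the main long-term comparison. Every subject is meant to complete that window. State the cut-off as a day or as the Week 24 visit; SAP 4.9.5 renumbers Day 0 as Study Day 1, so 24 × 7 = 168 days after treatment is Study Day 169.
2. Show events with onset after Week 24 separately, by arm.
3. Summarise length of follow-up by arm next to the injected volume in SAP 4.8.1.
4. Keep the whole-trial table, because that endpoint is named in Protocol 7.3 and SAP 3.3.1, with a footnote that follow-up after Week 24 depends on the efficacy outcome.
5. Treat exposure-adjusted rates as secondary at most, since they remove the bias fully only under a constant hazard.

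The cost is SAP wording, a date filter and one or two extra tables. Onset dates and visit dates are already collected, so no new data are needed, and the Week 4 tables and listings stay as they are.
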